# 4. Risks

There are no foreseeable risks. However, if subjects feel at all uncomfortable, they may cease participation at any time and forgo participation. Subjects' names will not appear anywhere on the surveys, but stored rather than dummy IDs that subjects generate themselves. Survey data for tracks [1-4] and health metric data will for tracks [2-4] will be stored on an encrypted computer owned by Tulane University using files that will be password protected. Electronic backup will be made to a secure shared drive hosted by Tulane University Information Technology Services. Only study staff will have direct access to the data. Only study staff will have access to the code key that identifies participants. This will be stored on a separate dataset on a secure, password protected Tulane hard drive. Subject survey responses are also protected by being collected through Qualtrics, an advanced online survey system used by research teams. Servers are protected by high-end firewall systems, and scans are performed regularly to ensure that any vulnerabilities are quickly found and patched. Complete penetration tests are performed yearly. All services have quick failover points and redundant hardware, with complete backups performed nightly. The confidential system component design uses multiple checks to certify that packets from one subsystem can only be received by a designated subsystem. Access to systems is severely restricted to specific individuals, whose access is monitored and audited for compliance. Customer data are stored in a specific location; it does not float around in the "cloud." In addition, all data are processed in that location, and are not moved to another jurisdictional area. In other words, if data are collected in the U.S., all data are processed in the U.S. Qualtrics uses Transport Layer Security (TLS) encryption (also known as HTTPS) for all transmitted data. Qualtrics also protects surveys with passwords and HTTP referrer checking. Qualtrics services are hosted by trusted data centers that are independently audited using the industry standard SSAE-16 method. Qualtrics deploys the general requirements set forth by many Federal Acts, including the FISMA Act of 2002. They meet or exceed the minimum requirements as outlined in FIPS Publication 200. Qualtrics safeguards all responder data, and uses secure data centers to ensure the highest protection as per requirements of HITECH (Health Information Technology for Economic and Clinical Health Act) to ensure that data are properly protected and best security practices followed. In the case of an emergency for the treatment group (though not expected), please exit GCCM through the labeled exits and follow the instructions of the class facilitators familiar with the facility.

# 5. Benefits

Subjects may benefit from the cooking classes or MNT sessions (control group for [4]) as they have both been shown to improve health, and society may benefit in general.

# 6. Remuneration

Version Date: 09/26/15 Version Number: 1 Page 4 of 9 There will be no payment for participation in this research study.

#### 7. Academic or Extra Credit

The GCCM classes will not affect the grades for trainees in [1] so that answers can be given without concern for their impact on grades (class instructors who control grades will not receive the survey responses). Marketing students who take the self-regulation survey can receive 1.33 credits for their marketing class based only on participation, and not for any particular responses so there be no pressure to answer in certain ways.

#### 8. Costs

There will be no costs to the subject for participating in this research study.

#### 9. Alternatives

The alternative is that the subjects do not have to participate in the research.

#### 10. Consent process and documentation

[1] Medical professionals track: A waiver of documentation of consent has been attached to this package for both medical professionals and trainees and marketing students, due to the information necessary for informed consent being provided in the recruitment email and the significant logistical challenges of documenting consent individually for such a large number of respondents remotely accessing the survey through the confidential online survey link. Email addresses are collected to verify the accuracy of the self-generated dummy IDs for subjects who respond to repeat surveys, and then the emails are deleted from the dataset used for longitudinal analysis.

[2] Community, [3] Employee, and [4] RCT tracks: A full description of the research will be discussed with subjects regarding both study groups. Discussion about the risks and benefits will be undertaken with prospective participants. This will mirror the written information in the consent form. After full information is discussed and questions are answered the participants the consent form will be reviewed and subjects will be asked to sign the form if they are interested in being involved (adults) or assent (children). Telephone numbers are collected based on GCCM experience over the past four years that class participants find reminders about classes helpful.

# 12. Survey links

[1] CHOP-Medical Professionals: http://tulane.qualtrics.com/SE/?SID=SV\_57Pu9twXUczA4gR.
[2-4] CHOP-Community, -Employees, -RCT Adults: http://tulane.qualtrics.com/SE/?SID=SV\_5C5tqoWuaGK4esR.
[2-4] CHOP-Community, -Employees Children: http://tulane.qualtrics.com/SE/?SID=SV\_08RuXreVqaFzV0F.
[Supplemental] Self-regulation: http://tulane.qualtrics.com/SE/?SID=SV\_beARYSuPFbCp9pH.

# **Statistical Analysis Plan**

# **Power Analysis**

The required calculated sample size to achieve 80% power and detect an odds ratio (OR) of at least 1.50 with a two-sided test set at 5% was 263 cases.

# Machine Learning and Statistical Analysis

The first phase of the analysis was conducted with ML within a supervised learning framework to test 43 algorithms with 10-fold cross-validation, selected based upon the data type. Algorithm performance was assessed favorably based on higher accuracy, lower root relative squared error (RRSE) with model acceptability set at 100% (for comparison among ML algorithms), and lower root mean squared error (RMSE, for comparison to traditional statistical models). Performance could be improved further if the relevant ML algorithms would be additionally permitted to select which variables should be included in the models. But to improve comparison to traditional statistical results, all the variables based on the above literature to be included in the statistical regression models were included first in the ML algorithms. The following algorithms by type were tested: Bayesian (Bayes Net, Naive Bayes, Naive Bayes Multinomial Text, and Naive Bayes Updateable), Functions (Logistic, Multilayer perceptron, SGD, SGD Text, Simple Logistic, SMO, and Voted Perceptron), Lazy (IBK, KStar, and LWL), Meta (AdaBoostM1, Attribute Selected Classifier, Bagging, Classification via Regression, CV Parameter Selection, Iterative Classifier Optimizer, Logit Boost, Multiclass Classifier, Multiclass Classifier Updateable, Multi-Scheme, Random Committee, Randomizable Filtered Classifier, Random Sub-Space, Stacking, Vote, and Weighted Instances Handler Wrapper), Miscellaneous (Input Mapped Classifier), Rules (Decision Table, JRip, OneR, Part, and ZeroR), and Trees (Decision Stump, Hoeffding Tree, J48, LMT, Random Forest, Random Tree, and REP Tree).

The second phase of analysis was conducted with traditional statistics using a novel integration of three statistical methods. Panel analysis of longitudinal data with triply robust propensity score (PS) adjusted multilevel mixed effects multivariable regression was conducted for causal inference. There is extensive, well-accepted statistical literature that causation can be inferred in observational trials without randomization through certain rigorous statistical methods, with fixed effects and propensity score being two of the most popular and well validated particularly with panel data.

Doubly robust estimation features a dual strategy of outcome regression that also accounts for the likelihood of receiving an exposure or treatment, such as with a PS. Simply using multivariable regression or PS analysis can lead to biased treatment estimates if either model is incorrectly specified. But with doubly robust estimation using both concurrently, only one model must be correctly specified to produce unbiased estimates. Of all the forms of PS analysis (i.e., matching, stratification, weighting, and adjustment), regression that includes the PS as one of the adjusted variables has quantitative evidence as being the top performing PS method. Finally, mixed effects regression further provides a powerful approach to causal inference. This mixed method contains both fixed effects (FE) and random effects (RE) components, with FE having the distinct advantage of controlling even for nonobserved traits by controlling for all time-invariant traits. FE does this by setting each individual subject as his/her own control and thus models within-person effects. Aside from the theoretical advantages, FE has shown quantitative strengths over competing methods. RE was used to control for what FE cannot,

Version Date: 09/26/15 Version Number: 1 Page 8 of 9 namely, time-varying traits at the individual level with repeated observations over time (as students progressed through their medical education). The multilevel aspect was used to account for the hierarchical nature of the data in which medical trainees responded from different medical institutions. Inverse-variance weighted fixed effects (IVWFE) meta-analysis was used to produce a composite estimate across the 25 competency topics.

This triply robust approach can be represented by the following mathematical formula:

$$\Pr(y_{ij} = 1 \mid u_j) = H(x_{ij}\beta + z_{ij}u_j)$$
(1)

for *M* independent clusters conditioned on random effects  $u_j$  for j = 1, ..., M clusters with cluster *j* constituting  $i = 1, ..., n_j$  observations, outcome  $y_{ij}$ , FE covariate  $x_{ij}$ , RE covariate  $z_{ij}$ , and regression coefficient  $\beta$ , all within a logistic regression equation with logistic cumulative distribution function of  $H(\bullet)$ . The PS is utilized as an additional variable in the above model and is represented as

$$e(x_i) = \Pr(z_i = 1 \mid x_i)$$
(2)

in which exposure probability is conditioned on the covariate  $x_i$  observed.

The competing causal inference methods of instrumental variable and difference in difference analyses were not utilized due to their methodological weaknesses, respectively, of having varying degrees of reliable instrumental variables and having a prevalence of unobserved confounders exerting time-varying effects before and after the exposure/treatment. The above methods of doubly robust PS adjustment in multivariable regression were therefore integrated with multilevel mixed effects to provide a novel triply robust approach to causal inference. Aside from controlling for the likelihood of receiving GCCM education (via the PS) and unobserved time-invariant traits (via FE) and time variant along with intracluster correlation (via RE), this integrative method controlled via regression for age, gender, race, prior nutrition education, special diet, school year, intended specialty, and medical school. This multilevel approach has a Bernoulli conditional distribution of the response given the random effects and logistic cumulative distribution function for the success probability.

All results are reported as fully adjusted ORs. ORs rather than relative risks were calculated due to the complex data source described above and due to the rare disease assumption. Statistical significance was set at a two-tailed *p* value < 0.05. ML analysis was performed in R 3.3.2 (The R Foundation for Statistical Computing, Vienna, Austria). Statistical analysis was performed in STATA 14.2 (STATACorp, College Station, Texas, United States of America). Ethics approval was obtained through the Institutional Review Board (IRB) of Tulane University.

Version Date: 09/26/15 Version Number: 1 Page 9 of 9

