CHOP is a prospective observational cohort study with four tracks ([1] medical professionals, [2] community, [3] employee, and [4] randomized controlled trial [RCT]) to allow results to be compared among the subjects in the four tracks. [1] Current and future medical professionals will be trained in classes within their track in how to educate patients about nutrition, and their results for their DACs will be compared to those who receive traditional clinical education. [2] Adults, adolescents, and children 7 years and older will be offered classes in their community track to allow comparison of their DACs and health metrics with those who do not take the classes. [3] Employees and their families who take the GCCM classes as employee wellness programing will have their DAC and health metrics compared to employees who do not take the classes. And finally, [4] subjects with such chronic health conditions as diabetes will be randomized with equal 50% chance to either taking the GCCM classes or receiving medical nutrition therapy (MNT) with a registered dietician (RD).

DAC surveys will take place for the first track at the beginning and end of each academic year. Surveys will take place for the last three tracks at the first and last class for the treatment (GCCM) class group, and the beginning of the study and 2-3 months later for the control groups (those who do not take the classes). The same adult and children surveys will be used across tracks [2]-[4] for adults 18 years and older and children 7-17 respectively. Medical professionals in [1] will have the same survey.

CHOP unites such analyses as diffusion of innovation (DOI), social network, and simulation-based medical education with deliberate practice (SBME-DP) along with rigorous statistical methods to answer these questions and hopefully benefit society. Results will be strengthened by using self regulation survey with Tulane marketing students to better design the DAC survey based on understanding what DACs predict

Version Date: 09/26/15 Version Number: 1 Page 2 of 9 certain nutrition behavior, in addition to comparison to the de-identified National Health and Nutrition Examination Survey (NHANES) for national trends in diet and similar health metrics and behaviors.

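### The machine-learning phase does not say that a trainee's repeat surveys stay in one cross-validation fold; if folds are drawn by survey, RRSE and accuracy can look favourable with no true predictor

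*Combined protocol and SAP*

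**What the plan says.** The SAP section Machine Learning and Statistical Analysis describes a "supervised learning framework to test 43 algorithms with 10-fold cross-validation, selected based upon the data type". Performance is judged by accuracy, by "lower root relative squared error (RRSE) with model acceptability set at 100% (for comparison among ML algorithms") and by "lower root mean squared error (RMSE, for comparison to traditional statistical models"). RRSE therefore has a pass level, while RMSE is a comparison only. The algorithms receive the same variables as the regression. The unit that is divided into folds is not stated, and grouping by person is mentioned nowhere.

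The same section calls the second phase "Panel analysis of longitudinal data with triply robust propensity score (PS) adjusted multilevel mixed effects multivariable regression" and assigns random effects to "time-varying traits at the individual level with repeated observations over time". Protocol section 1 gives the schedule: "DAC surveys will take place for the first track at the beginning and end of each academic year". Protocol section 10 says that self-generated IDs link the surveys of those who respond more than once. Within-person dependence is thus recognised, but it is handled only in phase two.

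**The concern.** Cross-validation estimates performance in new subjects only if the held-out subjects are new. The covariates are age, gender, race, earlier nutrition teaching, diet, year and school of training, and intended specialty. Most change little between two surveys of the same trainee, and together they come close to identifying that person. If folds are drawn by survey record, a random forest, bagged trees or a nearest-neighbour learner (IBK), all on the list, can match a held-out record to the same trainee's other records and repeat that trainee's answer. RRSE and accuracy then partly measure recognition of a known person. They no longer measure only whether the variables, including GCCM exposure, predict the outcome in an unseen trainee. At stake is any statement that the ML models are acceptable or predict well.

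**Working it through.** The plan gives no figure for this point. Its algorithm list does add up: 4 + 7 + 3 + 16 + 1 + 5 + 7 = 43.

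**Inputs.** From the documents: 10 folds, the RRSE level of 100%, the covariate list, two surveys offered per academic year, and repeat responders as a subset. Not in the documents, so assumed: the fold unit, within-person correlation (ICC), outcome rate, number of trainees, share repeating, and surveys per person.

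**Step 1: how often a person is split across folds.** With m surveys per person and record-level folds, the chance that at least one other survey is in training is about 1 − 0.1^(m−1). For m = 2 this is 0.90, and for m = 4 it is 0.999. Simulated splits gave 0.903 and 0.997.

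**Step 2: what recognition alone could achieve.** If the person were identified perfectly and k other answers were in training, with correlation ρ between two binary answers of one person, the best linear prediction gives RRSE = 100·√(1 − kρ²/(1 + (k−1)ρ)).
- ρ = 0: 100%.
- k = 1, ρ = 0.2: 100·√(1 − 0.04) = 98.0%.
- k = 3, ρ = 0.2: 100·√(1 − 0.12/1.4) = 95.6%.
- k = 3, ρ = 0.4: 100·√(1 − 0.48/1.8) = 85.6%.

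Any positive correlation therefore leaves room below 100% with no useful covariate.

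**Step 3: what real learners do under a null.** The binary outcome depended only on a trainee random intercept. There was no covariate or GCCM effect. The simulation used 300 trainees, all repeating, a 50% outcome rate and covariates patterned on the SAP's list. RRSE = 100·√(Σ(p − y)² / Σ(training mean − y)²). Six algorithms were run: logistic, naive Bayes, decision stump, 5-nearest-neighbour, and random forest with minimum leaf 1 and 3. With 16 runs per row, the standard error of a share is at most 0.5/√16 ≈ 0.12.

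| Surveys each | Latent ICC | Any of six below 100%, by record | Same, by trainee | Forest (leaf 3) mean RRSE, by record | Same, by trainee |
|---|---|---|---|---|---|
| 2 | 0 | 19% | 19% | 102.4 | 101.6 |
| 2 | 0.2 | 38% | 31% | 100.2 | 101.6 |
| 2 | 0.4 | 94% | 19% | 98.6 | 101.8 |
| 2 | 0.6 | 100% | 12% | 96.7 | 102.0 |
| 4 | 0 | 25% | 19% | 102.4 | 101.5 |
| 4 | 0.2 | 50% | 0% | 99.7 | 102.2 |
| 4 | 0.4 | 100% | 6% | 97.1 | 102.8 |
| 4 | 0.6 | 100% | 0% | 93.9 | 103.3 |

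At ICC 0.6, accuracy of the forest with minimum leaf 1 was 0.68 by record and 0.49 to 0.51 by trainee. Logistic regression averaged 100.2 to 102.0% by record at ICC 0.2 to 0.6, so the effect sits mainly in flexible learners.

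**Step 4: one algorithm alone.** For bagged trees (300 trainees, four surveys, ICC 0.5, 40 runs), mean RRSE was 96.9% by record and 105.8% by trainee. Accuracy was 62% and 50%, and the level was met in 40/40 and 0/40 runs. With two surveys (30 runs) it was met in 83% and 0%. The effect does not need a choice among 43.

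**Step 5: less favourable settings.** Share of runs below 100% with record-level folds for bagged trees, fully grown / minimum leaf 3 (300 trainees, 15 runs each):
- Two surveys, ICC 0.5, half repeating: 20% / 33%; 30% repeating: 0% / 7%.
- Four surveys, ICC 0.5, 30% repeating: 40% / 80%.
- Four surveys, ICC 0.3, all repeating: 0% / 60%.
- 10% outcome rate, ICC 0.5: four surveys 13% / 73%; two surveys 20% / 47%.

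Random forest (leaf 3), ICC 0.5, half repeating, 12 runs each, by record against by trainee:
- 300 trainees: 58% against 8% (two surveys), 100% against 8% (four).
- 1,000 trainees in five schools: 92% against 8% (two surveys), 100% against 0% (four).

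A further set of 8-run settings with the same forest (300 trainees), including 30 to 50% repeating, ICC 0.3 or a 10% outcome rate, gave 62 to 100% against 0 to 12%.

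**Step 6: what grouping leaves untouched.** With one survey per trainee, so no leakage, some algorithm still fell below 100% in 44% of runs. With grouped folds at ICC 0.2 to 0.6 this happened in 0 to 31%. The 100% level is simply the no-information level, and picking the best of many crosses it by chance.

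**The case against.** - **The fold unit is unstated.** A reader might infer that the plan divides surveys rather than people. The text does not say so. Record-level folds are only the ordinary form of the method when no grouping is given. This stands, and the point is conditional on it.
- **Not every trainee repeats.** Protocol section 10 treats repeat responders as a subset, and their share is not given. This stands. Step 5 shows that the effect can shrink to almost nothing with two surveys and 30% repeating, and can stay large with four surveys.
- **The assumed 50% outcome rate is not the plan's setting.** The SAP invokes a rare-disease assumption. At 10% the effect was smaller for fully grown trees but still present. A claim that the RRSE level can never discriminate is therefore not supported.
- **ML versus regression.** It is tempting to conclude that leakage ranks ML above regression. Bagging did beat plain logistic regression on RMSE in 40/40 runs by record and 0/40 by trainee (300 trainees, four surveys, ICC 0.5). But the plan's regression is a mixed model with individual-level terms. Under the same null, a person random-intercept model with known parameters had RRSE of about 73% in-sample and 88% when predicting each record from that person's others. Bagging had 96 to 99%, and fully grown trees beat the random-intercept model in 0/10 runs. The SAP also does not say whether the regression RMSE is cross-validated. The comparison is not like-for-like, but its direction of bias is not established.
- **Limited consequence.** The SAP reports fully adjusted odds ratios from phase two, and nothing in the documents uses ML to choose that model. This stands.

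**Conclusion.** The concern holds as a conditional one. The plan leaves open a choice that can decide the ML performance figures. Under the ordinary reading of that choice, RRSE and accuracy are optimistic for repeat responders, and the 100% level can be met when nothing predicts the outcome. In these simulations the effect is absent at ICC 0, variable at 0.2 to 0.3 or with few repeat responders, and strong from about 0.4 with most trainees repeating. The documents do not allow the ICC, the share repeating, the surveys per person or the selected learner to be fixed, so no single size can be given. The runs are few, and a handful of algorithms stand in for 43. RMSE has no pass level to be met. The phase-two odds ratios are not affected. The 100% cut-off and the selection among 43 algorithms are separate issues. Label: cheap improvement.

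**What to change.** In the first sentence of the SAP section Machine Learning and Statistical Analysis, replace the validation wording with: *10-fold cross-validation with folds formed by respondent (all surveys linked to one dummy ID in the same fold)*. Compute the comparison regression's RMSE on the same held-out folds, without the held-out person's own random effect. Base every RRSE, RMSE and accuracy statement on those folds.

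The linked ID already exists, so no new data are needed. The cost is one or two sentences, slightly more analysis work, and ML performance that will probably look less favourable. If folds were already formed by respondent, the new wording only records it.

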# 2. Subject Population

[1] Medical professionals track: All participants (over 17) who have matriculated to the Tulane University Health Sciences Center as students or residents in addition to physicians participating in the curriculum as continuing medical education (CME) credits for a target sample of 10,000 respondents. Subjects will be offered the survey from medical school through residency and into medical practice. Up to 1,000 marketing students will be offered a self-regulation survey.

[2] Community track: Adults 17 years and older and children 7-17 in the Greater New Orleans area for a target sample of 6,000 subjects (3,000 taking the classes and the rest not). Subjects will be followed for three years after their class participation or lack thereof based upon standards for such studies.

[3] Employee track: Employees and their family members 7 years and older affiliated with Laitram, LLC for a target sample of 3,000 subjects (1,500 taking the classes and the rest not). Subjects will be followed for three years after their class participation or lack thereof based upon standards for such studies.

[4] RCT track: Adults 17 years and older with diagnosed diabetes, hypertension, hyperlipidemia, cardiovascular disease, or past history of cerebrovascular disease or their pre-diagnosis conditions (i.e. pre-diabetes as the condition at risk for developing diabetes) for a target sample of 500 subjects. Subjects will be followed for three years after their class participation or lack thereof based upon standards for such studies.

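### The SAP does not say that a respondent's repeat surveys stay in one cross-validation fold, so ML accuracy can be overstated and the comparison with regression is hard to interpret

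*Combined protocol and SAP*

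**What the plan says.** The SAP, under Machine Learning and Statistical Analysis, describes two phases. The first is "to test 43 algorithms with 10-fold cross-validation", judged on accuracy and RRSE among the algorithms and on RMSE "for comparison to traditional statistical models". The ML models first receive the same variables as the regression, so that the two can be compared. The second phase is "Panel analysis of longitudinal data with triply robust propensity score (PS) adjusted multilevel mixed effects multivariable regression", whose random effects are meant to handle "time-varying traits at the individual level with repeated observations over time".

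Repeat surveys are part of the design. Protocol section 1 states: "DAC surveys will take place for the first track at the beginning and end of each academic year". Section 2 adds, for the medical professionals track: "Subjects will be offered the survey from medical school through residency and into medical practice". Section 10 describes an identifier that respondents create themselves and that is checked against their email address to link repeat surveys.

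Three things are not stated: whether folds are formed by survey row or by respondent, whether the ML data hold every repeat survey or one row per person, and whether the regression RMSE is held-out or in-sample.

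**The concern.** Cross-validation estimates performance on new people only if the held-out people are new. Plain 10-fold cross-validation partitions rows, and keeping a person's rows together is an extra step that a plan has to specify. The second phase models clustering explicitly. The first phase does not mention it.

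The shared predictors make recognition of a person plausible. Gender, race and medical school hardly change within a respondent. Intended specialty, special diet and earlier nutrition education may change, but usually slowly. Age and school year do move. A flexible learner that finds the same person's other survey in the training data can copy that answer and appear to predict well. The gain differs by algorithm, so it can alter the ranking as well as the level of accuracy.

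At stake are the reported ML accuracy, the choice among 43 algorithms, and the RMSE comparison with the traditional models.

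**Working it through.** **The plan's own figures.** The SAP gives no ML accuracy or RMSE to reproduce. The algorithm count does reproduce: 4 + 7 + 3 + 16 + 1 + 5 + 7 = 43. Three of these (IBK, KStar, LWL) are instance-based.

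**Inputs.** From the documents: 10 folds, and two surveys per academic year in the medical professionals track. Assumed: m = 2, 4 or 8 surveys per person (8 = 2 × 4 years of training) and a within-person ICC on the latent logit scale of 0.2, 0.4 or 0.6. Neither figure is in the documents.

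**Step 1: how often a row meets its own respondent.** With random row folds, the chance that at least one other survey from the same person is in training is about 1 − 0.1^(m−1).
- m = 2: 1 − 0.1 = 0.90
- m = 4: 1 − 0.001 = 0.999
- m = 8: practically 1

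**Step 2: what that does to accuracy.** The simulation used 1,600 rows, 8 replicates, covariates of the kind the SAP lists, and 10 folds formed by row or by respondent. Cells show accuracy by row / by respondent, with the difference in points in brackets (taken before rounding).

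| m | ICC | 1-NN | 5-NN | Logistic (ridge) |
|---|---|---|---|---|
| 2 | 0.2 | 0.568 / 0.516 (5.2) | 0.541 / 0.513 (2.8) | 0.544 / 0.539 (0.4) |
| 2 | 0.4 | 0.625 / 0.513 (11.2) | 0.553 / 0.510 (4.3) | 0.542 / 0.536 (0.6) |
| 2 | 0.6 | 0.681 / 0.504 (17.6) | 0.565 / 0.507 (5.8) | 0.542 / 0.523 (1.9) |
| 4 | 0.2 | 0.578 / 0.516 (6.2) | 0.583 / 0.525 (5.9) | 0.561 / 0.546 (1.6) |
| 4 | 0.4 | 0.636 / 0.516 (12.0) | 0.635 / 0.522 (11.3) | 0.564 / 0.536 (2.8) |
| 4 | 0.6 | 0.706 / 0.513 (19.3) | 0.684 / 0.515 (16.9) | 0.558 / 0.519 (3.9) |
| 8 | 0.2 | 0.587 / 0.518 (6.9) | 0.615 / 0.516 (9.9) | 0.569 / 0.531 (3.8) |
| 8 | 0.4 | 0.648 / 0.516 (13.1) | 0.685 / 0.517 (16.8) | 0.588 / 0.527 (6.1) |
| 8 | 0.6 | 0.711 / 0.515 (19.6) | 0.750 / 0.519 (23.1) | 0.603 / 0.517 (8.5) |

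With m = 1 or ICC = 0 the differences run from −1.6 to +0.4 points, which is noise.

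**Step 3: ranking.** On accuracy, 1-NN beats logistic in all nine settings with row folds and in none with respondent folds, although at m = 8 and ICC 0.6 the respondent-fold gap is only 0.515 against 0.517. On RMSE, at m = 4 and ICC 0.4, row folds favour 5-NN (0.491 against 0.496) and respondent folds favour logistic (0.506 against 0.556). The same RMSE reversal appears at m = 4 with ICC 0.6 and at m = 8 with ICC 0.4 and 0.6. It does not appear at m = 2 or at ICC 0.2.

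The logistic model here was scored inside the cross-validation. The SAP's mixed-effects regression was not simulated.

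**The case against.** The strongest reply is that the SAP is silent, and silence is not an error. The passage on repeated observations describes the regression, and the ML data may have held one row per person. A linking identifier existed, so folds by respondent were feasible. This stands: a reader might infer that respondents were in fact split across folds and that the ML accuracy is inflated, but the documents show neither.

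Other stronger readings also go beyond the text.
- **The regression RMSE is in-sample.** A reader might infer this from "ML analysis was performed in R 3.3.2" and the use of STATA for the regression. A software line does not show how an RMSE was computed.
- **The comparison favours ML.** Row leakage would flatter ML. An in-sample RMSE, or person-specific information in the regression, would flatter regression. These pull in opposite directions, and nothing in the documents gives the net effect.
- **Choosing the best of 43 adds optimism.** A calculation with 43 equally good algorithms (accuracy 70%, correlation 0.5 to 0.8) gives about 3 to 4 points at 263 rows and 1 point at 3,000. Equal skill is implausible for a list running from ZeroR to Random Forest, and the SAP does not say that only the winner's score is reported.
- **The study's conclusions are at risk.** The SAP reports adjusted odds ratios from the regression, which fold assignment does not touch.

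It is also fair that nearest-neighbour methods are the worst case: at two surveys per person the logistic inflation is only 0.4 to 1.9 points.

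What the reply does not remove is that the standard meaning of 10-fold cross-validation is a split of rows, the study is a panel, and the first phase makes no provision for that. The unevenness across algorithms is itself what can distort a ranking.

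**Conclusion.** The point holds conditionally. The plan specifies plain 10-fold cross-validation in a repeat-survey study, without stating the fold unit or a common held-out basis for the regression RMSE. If folds are by row and repeat surveys are kept, accuracy can be overstated by about 5 to 20 points for 1-NN, 3 to 23 for 5-NN and 0.4 to 9 for logistic. These ranges rest on the assumed ICC, the assumed surveys per person and simulated covariates, so the actual size is unknown and may be zero. The consequence is confined to the ML accuracy, the algorithm ranking and the ML-versus-regression RMSE comparison. A change is worthwhile because that comparison is one the SAP sets out to make and cannot be interpreted as specified.

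**What to change.** State in the SAP how many surveys per respondent enter the ML data, and assign the 10 folds by the linked respondent identifier so that all of a person's surveys fall in one fold. Compute the regression RMSE on the same held-out folds. A held-out respondent has no estimable person-specific effect, so use population-level predictions there, that is, the fixed part of the model only. If one best algorithm's score is to be reported, select it in an inner loop and report its outer-loop score.

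The cost is a re-run of the ML phase with a grouping variable, plus refitting the regression within folds for the RMSE. No new data are needed. The reported ML accuracy may be lower.
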